**Table 7. Scale for Fever: Substudy C**

$\geq 38.0\text{--}38.4^{\circ}\text{C}$ ( $100.4\text{--}101.1^{\circ}\text{F}$ )
$>38.4\text{--}38.9^{\circ}\text{C}$ ( $101.2\text{--}102.0^{\circ}\text{F}$ )
$>38.9\text{--}40.0^{\circ}\text{C}$ ( $102.1\text{--}104.0^{\circ}\text{F}$ )
$>40.0^{\circ}\text{C}$ ( $>104.0^{\circ}\text{F}$ )

### 8.3.6. Pregnancy Testing

Following screening, pregnancy tests may be urine or serum tests, but must have a sensitivity of at least 25 mIU/mL. Pregnancy tests will be performed in WOCBP at the times listed in the substudy SoA, immediately before the administration of each vaccine dose. A negative pregnancy test result will be required prior to the participant's receiving the study intervention. Pregnancy tests may also be repeated if requested by IRBs/ECs or if required by local regulations. In the case of a positive confirmed pregnancy, the participant will be withdrawn from administration of study intervention but may remain in the study if the single dose of study intervention has already been administered.

### 8.4. Adverse Events, Serious Adverse Events, and Other Safety Reporting

The definitions of an AE and an SAE can be found in [Appendix 3](#).

AEs may arise from symptoms or other complaints reported to the investigator by the participant (or, when appropriate, by a caregiver, surrogate, or the participant's legally authorized representative), or they may arise from clinical findings of the investigator or other healthcare providers (clinical signs, test results, etc).

The investigator and any qualified designees are responsible for detecting, documenting, and recording events that meet the definition of an AE or SAE and remain responsible to pursue and obtain adequate information both to determine the outcome and to assess whether the event meets the criteria for classification as an SAE or caused the participant to discontinue the study (see [Section 7.1](#)).

During the active collection period as described in Section 8.4.1, each participant will be questioned about the occurrence of AEs in a nonleading manner.

In addition, the investigator may be requested by Pfizer Safety to obtain specific follow-up information in an expedited fashion.

#### 8.4.1. Time Period and Frequency for Collecting AE and SAE Information

The time period for actively eliciting and collecting AEs and SAEs ("active collection period") for each participant begins from the time the participant provides informed consent, which is obtained before the participant's participation in the study (ie, before undergoing any study-related procedure and/or receiving study intervention), through and including approximately 1 month after the participant's study vaccination.

In addition, any AE occurring up to 48 hours after any subsequent blood draw or nasal swab collection must be recorded on the CRF.

SAEs will be collected from the time the participant provides informed consent through approximately 6 months after the participant's study vaccination, per the SoA in each substudy appendix.

Follow-up by the investigator continues throughout the active collection period and until the AE or SAE or its sequelae resolve or stabilize at a level acceptable to the investigator.

When a clinically important AE remains ongoing at the end of the active collection period, follow-up by the investigator continues until the AE or SAE or its sequelae resolve or stabilize at a level acceptable to the investigator and Pfizer concurs with that assessment.

For participants who are screen failures, the active collection period ends when screen failure status is determined.

If the participant withdraws from the study and also withdraws consent for the collection of future information, the active collection period ends when consent is withdrawn.

If a participant permanently discontinues or temporarily discontinues from the study because of an AE or SAE, the AE or SAE must be recorded on the CRF and the SAE reported via PSSA.

Investigators are not obligated to actively seek information on AEs or SAEs after the participant has concluded study participation. However, if the investigator learns of any SAE, including a death, at any time after a participant has completed the study, and they consider the event to be reasonably related to the study intervention, the investigator must promptly report the SAE to Pfizer via PSSA.

#### **8.4.1.1. Reporting SAEs to Pfizer Safety**

All SAEs occurring in a participant during the active collection period for SAEs (through approximately 6 months after the participant's study vaccination) as described in [Section 8.4.1](#) are reported to Pfizer Safety via PSSA immediately upon awareness and under no circumstance should this exceed 24 hours, as indicated in [Appendix 3](#). The investigator will submit any updated SAE data to the sponsor within 24 hours of its being available.

#### **8.4.1.2. Recording Nonserious AEs and SAEs on the CRF**

All nonserious AEs and SAEs occurring in a participant during the active collection period, which begins after obtaining informed consent as described in [Section 8.4.1](#), will be recorded on the AE section of the CRF.

The investigator is to record on the CRF all directly observed and all spontaneously reported AEs and SAEs reported by the participant.

As part of ongoing safety reviews conducted by the sponsor, any nonserious AE that is determined by the sponsor to be serious will be reported by the sponsor as an SAE. To assist in the determination of case seriousness, further information may be requested from the investigator to provide clarity and understanding of the event in the context of the clinical study.

#### **8.4.2. Method of Detecting AEs and SAEs**

The method of recording, evaluating, and assessing causality of AEs and SAEs and the procedures for completing and transmitting SAE reports are provided in [Appendix 3](#).

Care will be taken not to introduce bias when detecting AEs and/or SAEs. Open-ended and nonleading verbal questioning of the participant is the preferred method to inquire about AE occurrences.

#### **8.4.3. Follow-Up of AEs and SAEs**

After the initial AE or SAE report, the investigator is required to proactively follow each participant at subsequent visits/contacts. For each event, the investigator must pursue and obtain adequate information until resolution, stabilization, the event is otherwise explained, or the participant is lost to follow-up (as defined in [Section 7.3](#)).

In general, follow-up information will include a description of the event in sufficient detail to allow for a complete medical assessment of the case and independent determination of possible causality. Any information relevant to the event, such as concomitant medications and illnesses, must be provided. In the case of a participant death, a summary of available autopsy findings must be submitted as soon as possible to Pfizer Safety.

Further information on follow-up procedures is provided in [Appendix 3](#).

#### **8.4.4. Regulatory Reporting Requirements for SAEs**

Prompt notification by the investigator to the sponsor of an SAE is essential so that legal obligations and ethical responsibilities toward the safety of participants and the safety of a study intervention under clinical investigation are met.

The sponsor has a legal responsibility to notify both the local regulatory authority and other regulatory agencies about the safety of a study intervention under clinical investigation. The sponsor will comply with country-specific regulatory requirements relating to safety reporting to the regulatory authority, IRBs/ECs, and investigators.

Investigator safety reports must be prepared for SUSARs according to local regulatory requirements and sponsor policy and forwarded to investigators as necessary.

An investigator who receives SUSARs or other specific safety information (eg, summary or listing of SAEs) from the sponsor will review and then file it along with the SRSD(s) for the study and will notify the IRB/EC, if appropriate according to local requirements.

#### **8.4.5. Environmental Exposure, Exposure During Pregnancy or Breastfeeding, and Occupational Exposure**

Environmental exposure occurs when a person not enrolled in the study as a participant receives unplanned direct contact with or exposure to the study intervention. Such exposure may or may not lead to the occurrence of an AE or SAE. Persons at risk for environmental exposure include healthcare providers, family members, and others who may be exposed. An environmental exposure may include EDP, EDB, and occupational exposure.

Any such exposures to the study intervention under study are reportable to Pfizer Safety within 24 hours of investigator awareness.

##### **8.4.5.1. Exposure During Pregnancy**

An EDP occurs if:

- A female participant is found to be pregnant within 28 days after receiving study intervention.
- A male participant inseminates a female partner within 28 days after receiving study intervention.
- A female nonparticipant is found to be pregnant while being exposed or having been exposed to study intervention because of environmental exposure. Below are examples of environmental EDP:
  - A female family member or healthcare provider reports that she is pregnant after having been exposed to the study intervention by needlestick injury, inhalation, or skin contact.
  - A male family member or healthcare provider who has been exposed to the study intervention by needlestick injury, inhalation, or skin contact then exposes his female partner prior to or around the time of conception.

The investigator must report EDP to Pfizer Safety within 24 hours of the investigator's awareness, irrespective of whether an SAE has occurred. The initial information submitted should include the anticipated date of delivery (see below for information related to termination of pregnancy).

- If EDP occurs in a participant or a participant's partner, the investigator must report this information to Pfizer Safety via PSSA, regardless of whether an SAE has occurred. Details of the pregnancy will be collected after the start of study intervention and until 28 days after the study intervention. Beyond 28 days after the study intervention, any pregnancy that occurs will not be considered EDP for this study.

- If EDP occurs in the setting of environmental exposure, the investigator must report information to Pfizer Safety via PSSA. Since the exposure information does not pertain to the participant enrolled in the study, the information is not recorded on a CRF; however, a copy of the completed Vaccine SAE Report Form is maintained in the investigator site file.

Follow-up is conducted to obtain general information on the pregnancy and its outcome for all EDP reports with an unknown outcome. The investigator will follow the pregnancy until completion (or until pregnancy termination) and notify Pfizer Safety of the outcome as a follow-up to the initial EDP Supplemental Form. In the case of a live birth, the structural integrity of the neonate can be assessed at the time of birth. In the event of a termination, the reason(s) for termination should be specified and, if clinically possible, the structural integrity of the terminated fetus should be assessed by gross visual inspection (unless preprocedure test findings are conclusive for a congenital anomaly and the findings are reported).

Abnormal pregnancy outcomes are considered SAEs. If the outcome of the pregnancy meets the criteria for an SAE (ie, ectopic pregnancy, spontaneous abortion, intrauterine fetal demise, neonatal death, or congenital anomaly), the investigator should follow the procedures for reporting SAEs. Additional information about pregnancy outcomes that are reported to Pfizer Safety as SAEs follows:

- Spontaneous abortion including miscarriage and missed abortion should be reported as an SAE;
- Neonatal deaths that occur within 1 month of birth should be reported, without regard to causality, as SAEs. In addition, infant deaths after 1 month should be reported as SAEs when the investigator assesses the infant death as related or possibly related to exposure to the study intervention.

Additional information regarding the EDP may be requested by the sponsor. Further follow-up of birth outcomes will be handled on a case-by-case basis (eg, follow-up on preterm infants to identify developmental delays). In the case of paternal exposure, the investigator will provide the participant with the Pregnant Partner Release of Information Form to deliver to his partner. The investigator must document in the source documents that the participant was given the Pregnant Partner Release of Information Form to provide to his partner.

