#### **4.4. Choice of Contraception/Barrier Requirements**

BNT162b2 is approved for use without any contraceptive precautions. All study interventions included in this study are RNA-LNP vaccines utilizing modRNA. While there is no suspicion of human teratogenicity based on the intended pharmacology, some of the variant vaccine components under evaluation have not been administered to humans before and, therefore, contraception requirements have been included in this protocol.

See [Appendix 4](#) for contraception requirements.

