## 10.4. Appendix 4: Contraceptive and Barrier Guidance

### 10.4.1. Male Participant Reproductive Inclusion Criteria

Male participants are eligible to participate if they agree to the following requirements during the intervention period and for at least 28 days after the last dose of study intervention, which corresponds to the time needed to eliminate reproductive safety risk of the study intervention(s):

- Refrain from donating sperm.

PLUS either:

- Be abstinent from heterosexual intercourse as their preferred and usual lifestyle (abstinent on a long-term and persistent basis) and agree to remain abstinent.

OR

- Must agree to use contraception/barrier as detailed below:
  - Agree to use a male condom, and should also be advised of the benefit for a female partner to use a highly effective method of contraception as a condom may break or leak, when having sexual intercourse with a WOCBP who is not currently pregnant.

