### 10.4.2. Female Participant Reproductive Inclusion Criteria

The criteria below are part of inclusion criterion 1 (Age and Sex; [Section 5.1](#)) and specify the reproductive requirements for including female participants. Refer to [Section 10.4.4](#) for a complete list of contraceptive methods permitted in the study.

A female participant is eligible to participate if she is not pregnant or breastfeeding and at least 1 of the following conditions applies:

Is not a WOCBP (see definitions below in [Section 10.4.3](#)).

OR

- Is a WOCBP and agrees to use an acceptable contraceptive method during the intervention period (for a minimum of 28 days after the last dose of study intervention). The investigator should evaluate the effectiveness of the contraceptive method in relationship to the first dose of study intervention.

The investigator is responsible for review of medical history, menstrual history, and recent sexual activity to decrease the risk for inclusion of a woman with an early undetected pregnancy.

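### Protocol 8.4.5.1 ties one 28-day exposure-during-pregnancy limit to detection, insemination and occurrence, so a woman's pregnancy recognised after 28 days may not be classified as an exposure

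*Protocol*

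**What the plan says.** Protocol section 8.4.5.1 applies 28 days in four places:

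- Female participant: "A female participant is found to be pregnant within 28 days after receiving study intervention".
- Male participant: "A male participant inseminates a female partner within 28 days after receiving study intervention".
- Data collection: "Details of the pregnancy will be collected after the start of study intervention and until 28 days after the study intervention".
- Cut-off: "Beyond 28 days after the study intervention, any pregnancy that occurs will not be considered EDP for this study".

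The same section requires every EDP to be reported to the sponsor's safety group within 24 hours, with or without an SAE. It has the investigator follow the pregnancy to its end, and it treats abnormal pregnancy outcomes as SAEs.

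The 28 days also appears in the contraception rules. For men (section 10.4.1) it runs "for at least 28 days after the last dose of study intervention, which corresponds to the time needed to eliminate reproductive safety risk". For women (section 10.4.2) contraception is required "for a minimum of 28 days after the last dose of study intervention". Section 4.4 explains that contraception was required because "some of the variant vaccine components under evaluation have not been administered to humans before".

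Section 8.3.6 and the three schedules of activities (10.7.1.3, 10.8.1.3, 10.9.1.3) place the only scheduled pregnancy test at the first visit, before the dose. Further tests are possible if an ethics committee or local regulation asks for them. Contraceptive use is last confirmed at the 1-month visit, 28 to 35 days after vaccination.

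**The concern.** A limit meant to identify pregnancies exposed to the vaccine would ordinarily be attached to the pregnancy itself. Here the female wording attaches it to discovery, which must come after conception and depends on when the woman tests. The male wording has no such dependence. A partner's pregnancy from insemination on day 20 counts whenever it is found. A participant's own conception on day 20, found on day 40, does not count on the literal wording.

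What is at stake is classification. EDP status triggers the 24-hour report and the follow-up of the pregnancy to its outcome. Two sites reading the same section could handle the same woman differently. According to section 10.3.3, an EDP without an AE or SAE is not entered on the CRF, so an uncomplicated pregnancy judged not to be EDP has no specified reporting route.

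**Working it through.** The plan gives no figure to reproduce, so the check is a comparison of wordings followed by a sensitivity calculation. Days are counted from the dose, so day 28 means 28 days after vaccination.

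**1. Wordings applied to one case: conception on day 20, found on day 40.**

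| Sentence in 8.4.5.1 | Event that must meet the limit | Result |
|---|---|---|
| Female limb | Discovery | Day 40 is after day 28: not included |
| Male limb (partner's pregnancy, insemination on day 20) | Insemination | Day 20 is within 28 days: included |
| Cut-off sentence | Occurrence | Day 20 is not beyond 28 days: not excluded |

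The woman's pregnancy is neither brought in by the definition nor shut out by the cut-off. The section does not settle her status.

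**2. Scheduled chances to find a pregnancy by day 28.** The test is before the dose. In Substudies A and B and in Cohort 2 of Substudy C, the only follow-up visit before day 28 is at 6 to 8 days; Cohorts 1 and 3 add one at 12 to 16 days. None has a scheduled test. The 1-month window covers 8 possible days (28 to 35), of which one is no later than day 28. A pregnancy first found at that visit on days 29 to 35 already fails the female limb.

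**3. Share of in-window conceptions missed on the literal reading.**

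Assumptions, none of them from the documents: conceptions spread evenly over days 0 to 28, and a fixed lag of L days from conception to recognition.

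A conception on day c is found on day c + L. It is missed when c + L > 28, that is, when c > 28 − L. The share missed is L/28.

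| L (days) | Last conception day found by day 28 | Share missed |
|---|---|---|
| 7 | 21 | 7/28 = 25% |
| 10 | 18 | 10/28 = 36% |
| 14 | 14 | 14/28 = 50% |
| 18 | 10 | 18/28 = 64% |
| 21 | 7 | 21/28 = 75% |
| 28 | 0 | 28/28 = 100% |

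If the female limb were tied to conception, the share missed by definition would be 0% for every L.

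**4. Pregnancy already present at dosing.** If conception came k days before the dose, discovery falls on day L − k, which is after day 28 only if L > 28 + k. This case therefore needs a lag longer than any in the table. Section 10.4.2 does recognise that an early pregnancy may go undetected at inclusion, and the literal wording would leave out one that stayed unrecognised past day 28.

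**5. How far SAE collection reaches.** Section 8.4.1 collects SAEs for about 6 months. The last visit is 175 to 189 days after the dose, so a conception on day 20 is then 155 to 169 days old (175 − 20 and 189 − 20), which is before term. Later outcomes depend on EDP follow-up, or on the investigator learning of an SAE and judging it reasonably related to the vaccine.

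**The case against.** The strongest reply is that the section can be read as turning on conception. Its only exclusion concerns pregnancies occurring after 28 days, and the female wording may be a stock phrase: section 8.4.5.2 uses similar wording for breastfeeding, and 8.4.5.1 uses it for nonparticipants with no deadline. This stands to the extent that exclusion is not certain. It does not remove the defect, because the female limb as written still requires discovery within 28 days.

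Four stronger inferences are tempting, and the documents do not support them:

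- *Conceptions in the second half of the window go unreported.* That needs a lag of 14 days, and no lag is given. A claim that half to all are lost starts from the same assumption; shorter lags give 25% or 36%.
- *Nobody asks about pregnancy later.* Participants are told to call if pregnancy is known or suspected (5.3.1). Telehealth visits in Substudies A and C include a conditional review of pregnancy test results (10.7.8.1.2, 10.9.8.1.2). Reported amenorrhea or irregular periods must be evaluated for 6 months (10.7.8.5.11, 10.8.8.5.11, 10.9.8.5.12). These routes are partial: the scheduled telehealth visits are only for participants whose blood draws have stopped, and Substudy B lacks the telehealth item. They also inform the site without changing the classification.
- *Pregnancy details stop at day 28.* Follow-up of an EDP to the end of the pregnancy shows that the 28 days is more naturally a qualifying window, though the sentence does not say so.
- *Abnormal outcomes would be lost.* Within about 6 months they are SAEs whatever the EDP status.

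It is also fair that section 10.4.1 gives the risk-elimination rationale for men only. Reading 28 days as the risk window for women is an inference from the matching contraception period and from 8.4.5.1 itself.

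**Conclusion.** The point holds as an inconsistency in a safety-reporting definition that can misclassify exposures. It is not a demonstrated exclusion. What may be lost is the 24-hour EDP report and the follow-up to outcome for a female participant whose qualifying pregnancy is recognised after day 28.

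The proportion affected on the literal reading rests entirely on the assumed lag and on even spacing of conceptions. The absolute number cannot be computed from the documents. It should be small, since women test negative before the dose and agree to contraception for at least 28 days. No efficacy, immunogenicity or primary safety estimand is affected. The change is still worth making, because each case is an exposure to a variant-adapted construct and the remedy is light.

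**What to change.** 1. In Protocol 8.4.5.1, reconcile the three triggers with each other and with the 28 days in 10.4.1 and 10.4.2. Make the female limb, like the male limb, turn on the biological event: pregnant at vaccination, or estimated conception within the existing 28-day window, whenever the pregnancy is found during study participation. The length of the window does not change.
2. State that the 28 days in the data-collection sentence is the qualifying window and does not limit the collection of pregnancy details, in line with the follow-up already required.
3. For participants still in follow-up in Substudy C, ask women of childbearing potential at the existing 3- and 6-month visits (C5, C6) whether a pregnancy has been found since vaccination and its estimated conception date. The same question in Substudies A and B is probably moot at this amendment: section 10.9.4.3 describes all Substudy A participants as dosed, and section 2.2.1 reports 1-month results for Substudy B.

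The cost is a wording change, one question at two existing visits, and a few more EDP reports to follow. No test or visit is added.
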